All drug compliance records will be kept current and will be made available for inspection by regulatory agency inspectors. Study drug will be given to patient at the baseline visit, and preferably at 6 month intervals thereafter. Instructions for shipping study drug to patients are provided in the appendix.

B.9. Study Timeline

There are two in-person study visits (baseline and 78 week follow-up) when patients will undergo vwMRI, approximately 60 minutes long, with a simultaneous clinical evaluation by a study investigator physician and blood draw. Every 2-4 months, the study coordinator will determine medication adherence, adverse events, or patient-reported recurrent stroke (see **Figure 1**).

	Screen/ Baseline	Day 1	Day 60	Day 120	Day 180	Day 240	Day 320	Day 480	Day 546
Informed Consent	Х								
Medical History/Current medications	х		х	х	х	Х	х	х	х
Vitals	Х								Х
Review CTA or MRA ¹	х								
Vessel wall MRI		Х							Х
Pregnancy test	Х								
Creatinine	Х								Х
Lipid panel	Х								Х
Lipoprotein (a)	Х								Х
Apolipoprotein B	Х								Х
Physical exam	Х								Х
Neurological exam	Х								х
NIHSS	Х								Х
Modified Rankin Scale	х								Х
Stroke adjudication			Х	Х	Х	Х	Х	Х	Х
Adverse event determination			х	Х	х	Х	х	х	х
Serious adverse events			Х	Х	Х	Х	Х	Х	Х

Figure 1: Schedule of Activities

1. To confirm ICAD of a major intracranial artery

B.10. Study Duration

- Estimated duration of research (study start to final study deliverable): 2 Years / 6 Months
- Estimated duration of first patient enrolled to last patient out: 2 Year / 0 Months
- Estimated duration for Amgen to supply study drug: 2 Year / 0 Months

C. Study Endpoints

C.1. Primary Endpoints

The primary endpoints are nominal change in the stenosis and percent atheroma volume (PAV) of cerebrovasculture arteries from baseline to week 78. We will use measure stenosis and PAV on vessel wall MRI (vwMRI), which evaluates all arteries from the aortic arch to the distal intracranial vasculature in a single scan. The primary endpoints will be analyzed for both: 1) all intra- or extracranial arteries that have at least 25% stenosis, and 2) seperately for the intracranial arteries. Stenosis and PAV will be measured using standard methodology.

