
C.2.a. Secondary endpoint 1 measurement:

a) ICAD post-contrast plaque enhancement (PPE): is a dichotomous variable evaluated on the T1 pre- and post-gadolinium sequences, with multiplanar reconstruction so the ICAD can be seen in cross section.²⁶ PPE is defined by placing a region-of-interest over areas of gadolinium enhancement in ICAD to evaluate if it is equal to or exceeds the signal intensity of the pituitary infundibulum, as previously described.²⁷

- b) Carotid intraplaque hemorrhage (IPH): MPRAGE positive plaque is defined as voxels with at least 2-fold signal intensity compared to sternocleidomastoid muscle as previously described. MPRAGE positive plaques can be reliably identified. Kappa values for inter- and intra-rater reliability for detection of MPRAGE positive plaque were 0.806 and 0.818 respectively (very good agreement).^{28,29}
- c) MRA Flow Dynamics (**MFD**): We will measure MFD using accepted quantitative MRA methodology. The VERiTAS study provided prospective confirmation of the importance of MFD as a biomarker of stroke risk for patients with ICAD. Given that MFD can easily be measured in our vwMRI protocol, we will acquire the data required for its quantification.

C.3. Secondary endpoint 2

To better understand the mechanism of Repatha's effect on intra- and extracranial atherosclerosis, we will measure the endpoint of change in cholesterol markers [LDL-C, HDL-C, lipoprotein (a), apolipoprotein B, and triglyceride level]. The change in cholesterol markers will be correlated with the primary and secondary study endpoints on vwMRI. Cholesterol values will be measured at the baseline and comparison MRIs, which are 78 weeks apart. If standard of care lab values are available within 30 days of the study visit, they can be used in place of the study lab value. An additional exploratory outcome that we will measure is the composite endpoint of "recurrent stroke," which encompasses new patient-reported symptomatic ischemic stroke, transient ischemic attack, or asymptomatic strokes that emerge between MRIs.

C.3.a. Secondary endpoint 2 measurement:

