We power our study on the primary endpoint of change in stenosis and PAV. The GLAGOV trial showed 0.95% reduction in PAV for patients randomized to Repatha versus a 0.05% increase in PAV for patients in the placebo arm and was 78 weeks in length. Because the major intracranial arteries have a similar luminal diameter to coronary arteries, we may reasonably expect a 1% reduction in PAV for our 78 week study as documented in previous literature. Patients with intracranial atherosclerosis can be expected to have at least 3 additional sites of atherosclerosis, including extracranial arteries, that will be included in the series of PAV outcomes. Each subject will provide four sites of atherosclerosis and therefore, 4 PAV measurements. This cluster designed study will be modeled by a mixed effects linear regression to account for the cluster of arteries per patient. We obtain >80% power for our sample size of 150 patients, two-sided significance level 0.05, and a conservative assumed standard deviation of 4% from previous studies for the assumed 1% reduction in PAV against the documented control PAV of 0%.²³ With 150 patients, the minimum effect size possible to detect with 80% power is a 0.51% reduction. A 0.50% difference has been reported to be the cutoff to distinguish individuals that experience cardiovascular events versus those who do not.²³ Assuming a withdrawal rate of 25-30%, we would still reach >90% power for a 1% reduction with the above-listed conditions. We do not expect to show a significant reduction in recurrent stroke, but anticipate seeing a trend towards that outcome. This data could be used to accurately construct and power a subsequent trial with the primary outcome of recurrent stroke. Finally, in GLAGOV the linear relationship between change in stenosis, PAV and on-treatment LDL-C was very robust. We will be replicate this finding through means of a generalized linear mixed effects model. Our effective sample size may be sufficiently large enough to match the GLAGOV trial as each patient will be able to contribute an average of 4 arteries giving us an expected sample size between 800 and 1200 dependent on a conservative prediction of intra-class correlation. All reported p-values will be twosided and deemed significant at the 0.05 level.

D.3. Loss to Follow-up

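### D.2's effective sample size of 800 to 1200 does not follow from 150 patients with four arteries each: the count is 600 change values at most, and the 0.51% in the same section implies about 483

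*Combined protocol and SAP*

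**What the plan says.** The trial enrols 150 patients in a single arm (B.2). Section C.1 defines the outcome: "The primary endpoints are nominal change in the stenosis and percent atheroma volume (PAV) of cerebrovasculture arteries from baseline to week 78". The LDL model in D.1 also takes change in stenosis or PAV as its outcome.

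Section D.2 makes these statements about the amount of data:

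- Sites per patient: "Patients with intracranial atherosclerosis can be expected to have at least 3 additional sites of atherosclerosis, including extracranial arteries", and then "Each subject will provide four sites of atherosclerosis and therefore, 4 PAV measurements".
- Precision, under an SD of 4% and a two-sided 0.05 level: "With 150 patients, the minimum effect size possible to detect with 80% power is a 0.51% reduction".
- Loss: "Assuming a withdrawal rate of 25-30%, we would still reach >90% power for a 1% reduction with the above-listed conditions".
- Effective sample size, in the sentence on the LDL–plaque relation: each patient will "contribute an average of 4 arteries giving us an expected sample size between 800 and 1200 dependent on a conservative prediction of intra-class correlation".

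D.2 says that a mixed model will handle the clustering of arteries within patients. It gives no ICC value.

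**The concern.** An effective sample size adjusted for positive within-patient correlation cannot exceed the number of values analysed. On D.2's own inputs that number is 600, yet even the lower end of its range is 800, although the range is said to rest on a conservative ICC. The same section gives a detectable reduction that implies a third, smaller figure.

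What is at stake is narrow. The range is the stated basis for the remark that this trial may match the coronary imaging trial on the LDL–plaque relation. D.2 also says that the trial's data could be used to power a later trial, so an overstated effective size and an unstated ICC could be carried forward.

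**Working it through.** **Inputs.** N = 150 patients (B.2, D.2); m = 4 arteries per patient (D.2); one change value per artery (C.1, D.1); SD 4%, two-sided 0.05, 80% power, fixed reference of 0% (D.2); loss 25–30% (D.2, D.3). The ICC is not given, so it is varied or solved for.

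**Formulas.**

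- Effective size: n_eff = N·m / (1 + (m − 1)·ICC)
- Detectable reduction (one-sample, normal approximation): (1.960 + 0.842) × 4 / √n_eff

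**1. The plan's 0.51%.** Solving for n_eff gives (2.802 × 4 / 0.51)² ≈ 483 (473 to 492 allowing for rounding of 0.51). With 150 patients and four arteries, 600 / 483 = 1.243, so ICC = 0.243 / 3 ≈ 0.08 (0.073 to 0.089 with rounding). The 0.51% is therefore reproducible with a small positive ICC and no loss. Counting one value per patient would give 2.802 × 4 / √150 = 0.915%, so 0.51% must rest on several arteries per patient.

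**2. The plan's 800 to 1200.** The count at ICC 0 is 150 × 4 = 600.

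| ICC (assumed) | n_eff, 150 completers | n_eff, 25–30% lost, not replaced |
|---|---|---|
| 0 | 600 | 450–420 |
| 0.1 | 462 | 346–323 |
| 0.2 | 375 | 281–263 |
| 0.5 | 240 | 180–168 |

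Reaching the stated range with four arteries needs a negative ICC: (600/800 − 1)/3 = −0.083 and (600/1200 − 1)/3 = −0.167. At ICC 0 it needs 800/150 = 5.3 to 1200/150 = 8 arteries per patient. Relative to 600, the range is 800/600 = 1.33 to 1200/600 = 2 times too large.

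**3. The two figures side by side.**

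| n_eff | Detectable reduction at 80% power |
|---|---|
| 420 | 0.55% |
| 450 | 0.53% |
| 483 | 0.51% |
| 600 | 0.46% |
| 800 | 0.40% |
| 1200 | 0.32% |

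The 0.51% and the 800 to 1200 cannot describe the same data.

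**4. Where the range may have come from.** Counting both scans gives 150 × 4 × 2 = 1200, and with eight values per patient an ICC of about 0.07 brings this to 1200 / (1 + 7 × 0.0714) = 800. Counting the two endpoints together also gives 1200. D.2 states neither. Neither is an effective size for a change outcome: two scans of an artery form one change, and stenosis and PAV are separate endpoints.

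**5. Effect on the main power statements.** For a 1% reduction, 80% power needs n_eff = (2.802 × 4)² ≈ 126. With 150 completers even an ICC of 1 leaves 150 (power 86%). For 90% power, n_eff = ((1.960 + 1.282) × 4)² ≈ 168. After unreplaced loss this is met up to an ICC of (450/168 − 1)/3 ≈ 0.56 at 25% loss and (420/168 − 1)/3 ≈ 0.50 at 30%.

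**The case against.** The best defence is that the range supports one hedged sentence about a supportive analysis, that four is not a ceiling because D.2 speaks of at least three further sites, and that B.7 and D.3 allow replacement or extra enrolment. The first part stands and limits the weight of the point. The other two do not rescue the range: the sentence derives it from an average of four arteries, and replacement that restores 150 completers restores 600, not 800. Nor does the LDL analysis supply more data: "Cholesterol values will be measured at the baseline and comparison MRIs, which are 78 weeks apart", so each patient has one on-treatment lipid value.

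A reader might infer more than the documents support:

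- *That the trial is underpowered or 150 is the wrong number.* Step 5 shows otherwise for the 1% effect, with the after-loss claim holding up to an ICC of about 0.5.
- *That 0.51% is mislabelled or that D.3's loss allowance is false.* D.2 ties 0.51% to 150 patients and ties the loss to the 1% effect. Nor can one say outright that 0.51% is incompatible with the full loss: at ICC 0, 483 values would come from 4.3 arteries per patient after 25% loss or 4.6 after 30%. It is incompatible only at exactly four arteries and a non-negative ICC.
- *That power for 0.50% falls short of a promise.* D.2 says "A 0.50% difference has been reported to be the cutoff to distinguish individuals that experience cardiovascular events versus those who do not". That is a value separating individuals, and the plan claims no power for a mean change of that size.
- *That the LDL slope suffers the same design effect as the mean change.* It depends on the residual ICC once LDL-C is fitted, which need not be equal.
- *That the comparison with the coronary trial is false.* That trial's sample size is not in the documents, so only the stated basis can be rejected.

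**Conclusion.** The range of 800 to 1200 is an arithmetic error on D.2's own inputs. The count is 600 at ICC 0, lower with any positive ICC, and 450 to 420 at ICC 0 if the planned loss is not replaced. The range also contradicts the 0.51% in the same section, which implies about 483.

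The 600 rests on 150 patients, an average of four arteries and one change value per artery. The 483, and the ICC of about 0.08 that goes with it, also take the 4% as the SD of one artery's change and the test as one-sample against a fixed 0%. The ICC is inferred from 0.51%; the plan does not state it.

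The severity is minor. The figure does not determine the sample size, and the power statements for a 1% reduction are unaffected within the ICC limit given above.

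**What to change.** In D.2:

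1. Replace the range of 800 to 1200 with: *about 600 change measurements at an average of four arteries per patient (about 420 to 450 if 25–30% are lost and not replaced), reduced further by the ICC.*
2. State the ICC used, so that this count and the 0.51% rest on the same value.
3. Recalculate the remark about matching the coronary imaging trial on the corrected size, or withdraw it.
4. Optionally, note that 0.51% assumes 150 completers, and that with four arteries and 25–30% unreplaced loss the detectable reduction is at least 0.53–0.55%.

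The cost is a few lines of text and one stated assumption. No extra patients and no rewrite of D.3 are needed.

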Proprotein convertase subtilisin/kexin type 9 (PCSK9) inhibitors, by modifying LDL receptors, have been shown to dramatically lower LDL. There is robust evidence that lowering LDL cholesterol is beneficial in atherosclerotic disease, due to plaque-stabilizing effects. The FOURIER and ODYSSEY studies showed that patients randomized to PCSK9 inhibition had dramatic LDL reduction and a lower overall incidence of stroke (1.2 versus 1.6% of patients over three years). The GLAGOV study showed that, compared to placebo, evolocumab (Repatha) decreased coronary artery plaque volume. GLAGOV also demonstrated a linear relationship between LDL cholesterol reduction and plaque volume regression. However, these findings do not provide adequate evidence that Repatha reduces the risk of ICAD stroke. FOURIER and ODYSSEY did not adjudicate the etiology of stroke and, for the stroke outcome, they included cardioembolic and lacunar strokes, which typically account for up to 50% strokes. The risk reduction from a PCSK9 inhibitor like Repatha would primarily be for patients with large artery atherosclerosis, such as ICAD. As a result, the absolute risk reduction seen in those studies does not represent the potential of Repatha in a patient population at risk for stroke.

A.3. Repatha

Repatha is an FDA-approved PCSK9 inhibitor shown to reduce the risk of cardiovascular events, including myocardial infarction, stroke, and coronary revascularization. Repatha is a patient-administered subcutaneous injection that is well tolerated. Common side effects include flu-like symptoms, cough, back pain, and dizziness. Further information can be obtained at: (https://www.pi.amgen.com/~/media/amgen/repositorysites/pi-amgen-com/repatha/repatha_pi_hcp_english.pdf).

A.4. Stenosis and Plaque Atheroma Volume Measured on vwMRI

We will measure both stenosis and atheroma volume to have two primary outcomes with validated biomarker potential. Stenosis is measured using WASID criteria.¹³ Atheroma volume is either directly measured or inferred by measuring the area of entire vessel (the outer wall boundary area) on an axial slice and subtracting the lumen area. In a study of middle cerebral artery ICAD, the atheroma volume on vwMRI was larger in the 26 symptomatic patients compared to the 35 asymptomatic patients (12.9±3.1 mm² vs. 8.2±3.6 mm², p<0.001). A second study enrolled 139 patients with moderate to severe middle cerebral artery atherosclerosis, who contributed 112 culprit and 53 non-

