culprit lesions.²² The combination of stenosis + atheroma burden + luminal area produced an odds ratio of 3.99 (95% CI: 1.74-9.13, p=0.001) for culprit plaque. The GLAGOV study showed that PCKS9 inhibition reduced the percent atheroma volume of coronary arteries over a 78 week treatment period.²³ With atheroma volume now established as a viable biomarker, vwMRI is the optimal test to monitor it and stenosis, both for ICAD and in other locations of the cerebrovasculature, such as the carotid arteries, cervical vertebral arteries, and aortic arch.

A.5. Impact

The result of this study will be a dataset that lays the foundation for a randomized controlled trial of Repatha in ICAD patients. The data collected in this study will allow us to optimize a future clinical trial designed to demonstrate a reduction in stroke risk, ultimately making more efficient and economical progress towards our ultimate research goal of preventing stroke with Repatha. While we are proposing future studies to reduce ICAD stroke risk, it should be noted that our study will also evaluate the potential for Repatha to decrease cerebrovasculature stenosis and plaque burden, which would be a compelling primary prevention indication.

B. Approach

B.1. Study Hypothesis

We hypothesize that inhibition of PCSK9 with Repatha in patients with moderate to severe intracranial atherosclerosis will reduce validated biomarkers of stroke risk (stenosis and percent atheroma volume). To answer our hypothesis, we propose a single arm study of Repatha in 150 patients with a prior history of ischemic stroke and ICAD causing at least 50% stenosis of a major intracranial artery in the Circle of Willis ("index artery").

B.2. Study Design

We will enroll 150 ICAD patients with a prior history of ischemic stroke. Patients will be enrolled at up to 8 medical centers in North America. All patients will receive Repatha for 78 weeks and will have an MRI before beginning study medication and a comparison MRI immediately after completing study medication.

B.3. Investigational Treatment

The investigational treatment is Repatha 140 mg administered subcutaneously with a single-dose pre-filled pen syringe every 2 weeks for a total of 39 treatments. Dose modification is not allowed.

B.3.a. Inclusion Criteria

- Adult patients, ≥ 18 years of age

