We will fit a mixed effects linear regression model, specifically a LOESS smoothing curve, to change in stenosis/PAV and on-treatment LDL-C, HDL-C, and lipoprotein(a). We will also use a multivariable linear regression model with the outcome of the primary endpoints, adjusted for covariates that could be confounders such as age, gender, smoking, statin use/dose and relevant medical comorbidities. The primary endpoints will also be compared to an assumed value of 0% change in stenosis and PAV that would correspond to optimal medical management without a PCSK9 inhibitor. Although, some studies have suggested statin therapy can reduce carotid atherosclerosis, no such effect is known for ICAD. For this analysis, we will use linear mixed effects model to detect differences in the stenosis and PAV endpoints between patients taking Repatha or the presumed historical control values of 0% change. For the secondary endpoints, we will use logistic and linear regression depending on the nature of the variable and use the primary predictors of on-treatment LDL-C, HDL-C, and lipoprotein(a). For the exploratory endpoint of recurrent stroke, we will use the above mentioned methods as well as a Cox proportional hazards model for the endpoint of recurrent stroke with the observed rate in this study compared to controls matched according to degree to stenosis of the index artery. Due to differences in arterial structure and flow dynamics, there may be a more significant plaque reduction in certain intracranial vessels. We anticipate subgroup analyses, for example comparing change in stenosis or PAV in the middle cerebral artery versus the vertebral artery.

D.2. Power Analysis

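### Two primary endpoints, each analysed in two artery sets, are all judged at two-sided 0.05, with no explicit rule for what counts as success

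*Combined protocol and SAP*

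**What the plan says.** Section A.4 announces "two primary outcomes with validated biomarker potential". Section C.1 defines them: "The primary endpoints are nominal change in the stenosis and percent atheroma volume (PAV) of cerebrovasculture arteries from baseline to week 78". It then sets two artery sets: "The primary endpoints will be analyzed for both: 1) all intra- or extracranial arteries that have at least 25% stenosis", and separately the intracranial arteries.

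Among several models, D.1 gives the comparison with a historical reference: "The primary endpoints will also be compared to an assumed value of 0% change in stenosis and PAV". Two endpoints in two sets make four comparisons with 0%. D.2 sets the only significance criterion in the document: "All reported p-values will be twosided and deemed significant at the 0.05 level".

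Some text bears on how the four results might combine.
- **Both endpoints.** The hypothesis in B.1 joins "validated biomarkers of stroke risk (stenosis and percent atheroma volume"), and D.2 uses the singular: "We power our study on the primary endpoint of change in stenosis and PAV".
- **Pooled set.** C.1 lists it first, C.1.a refers to a composite outcome computed from vessels above 25% stenosis, and D.2 counts four sites per patient, extracranial ones included.
- **Intracranial set.** B.1 frames the hypothesis around patients with intracranial atherosclerosis.

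None of these is written as a decision rule. The document gives no testing order, no division of alpha and no statement on either versus both.

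**The concern.** With four primary comparisons, one threshold and no combining rule, the meaning of a positive study can be settled after the results are known. A significant result for intracranial stenosis alone, or for pooled PAV alone, would each meet the only criterion in D.2. How far the false-positive rate exceeds 5% depends on a rule that the plan does not give.

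A.5 says that the data will lay the foundation for, and help optimise, a later randomized trial. A chance finding could therefore affect whether that trial goes ahead, or the assumptions used to plan it.

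**Working it through.** **Inputs from the plan (D.2).** 150 patients, 4 sites each, SD 4%, a 1% PAV reduction against 0%, two-sided 0.05, minimum detectable reduction 0.51% at 80% power, withdrawal 25-30%. An intra-class correlation (ICC) is mentioned without a value.

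**Reproducing the plan's figures.** Power = Φ(δ√Neff/SD − z), with Neff = patients × 4 / (1 + 3 × ICC).
- Even with one measurement per patient (Neff = 150), power for 1% is Φ(√150/4 − 1.960) = Φ(1.10) = 86.5%, so the claim of more than 80% holds.
- The 0.51% figure needs Neff = ((1.960 + 0.842) × 4 / 0.51)² ≈ 483 of 600 sites. The implied ICC is (600/483 − 1)/3 ≈ 0.08.
- These figures are for PAV across four sites. D.2 gives no effect size or SD for stenosis, and no calculation for the intracranial set.

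**Error rate under each possible rule.** The documents give no correlation between the four test statistics. I assumed 0.5-0.9 between artery sets (the intracranial arteries are part of the pooled set) and 0.3-0.9 between endpoints. For each combination I drew 2,000,000 sets of four normal statistics with a product correlation structure and counted |z| > 1.96.
- **Any one of four counts:** 9.7% (correlations 0.9 and 0.9) to 16.9% (sets 0.5, endpoints 0.3). Counting only false reductions, 4.9% to 8.5%, against a nominal 2.5%. For reference, four independent tests give 1 − 0.95⁴ = 18.5%.
- **Both endpoints in the same set, either set, all four nulls true:** 0.8% (sets 0.9, endpoints 0.3) to 5.5% (sets 0.5, endpoints 0.9).
- **The same rule, when one endpoint truly changes and is significant in both sets:** the other, null endpoint has two chances, giving 7.0% (sets 0.9) to 9.1% (sets 0.5).
- **Both endpoints in one named set:** 0.5% to 3.0% when both nulls are true, and at most 5% in any case.

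**Cost of the two remedies for pooled PAV.**
- Fixed sequence: the first test stays at 0.05, so the D.2 power for it is unchanged.
- Holm: the first step uses 0.05/4 = 0.0125, z = 2.498. The detectable difference becomes 0.51 × (2.498 + 0.842)/(1.960 + 0.842) = 0.51 × 1.19 ≈ 0.61%.
- Power at that Holm step for a 1% reduction, with 112.5 and 105 patients left after 25% and 30% withdrawal: 98.8% and 98.2% at ICC 0.08, 91.1% and 88.9% at ICC 0.3, 80.4% and 77.1% at ICC 0.5.

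**The case against.** The strongest reply is that the 10-17% belongs to a reading the plan never states. B.1 joins the two biomarkers with *and*, and D.2 speaks of one primary endpoint made of both. If both must succeed, the error is mostly below 5%, and if the pooled set also leads, it cannot exceed 5%. The emphasis on the pooled set in C.1, C.1.a and D.2 supports that lead. This stands as a limit on the size of the problem. It does not supply the rule, because A.4 and C.1 use the plural and B.1 points towards intracranial disease.

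A second reply is that this is a single-arm study meant to produce a dataset, where four related estimates with nominal p-values would be acceptable if labelled so. That is fair, and it lowers the weight of the point. But the plan does not label them so: it attaches a hypothesis, a power claim and a significance threshold to these endpoints.

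Third, D.1 introduces the 0% comparison after the lipid and covariate-adjusted models and never names a primary model. I treat it as primary because it is the comparison that D.2 powers.

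Two stronger readings are tempting. A reader might infer that a false positive would decide the endpoint of the next trial. D.2 already names recurrent stroke as that trial's primary outcome. A reader might also infer that the plan gives no hint of a lead artery set. It leans towards the pooled set in three places, without making that a rule.

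**Conclusion.** The point holds in a conditional form. The plan sets up four primary comparisons, applies 0.05 to each, and does not state how they combine. The familywise error is about 10-17% only if any one result is accepted as success. It is about 0.8-5.5% if both endpoints are required in the same set, either set, with all nulls true, and 7-9% in the less favourable case where one endpoint truly changes. It would be wrong to read 10-17% as the error rate of this plan, since the documents do not adopt that rule. They do not exclude it either, and the 0.05 rule in D.2 permits it.

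All ranges rest on the assumed correlations and on 0% being the true change without the drug. D.1 itself concedes that "some studies have suggested statin therapy can reduce carotid atherosclerosis, no such effect is known for ICAD". If the 0% reference is wrong for some arteries, no multiplicity rule corrects that. The change should be made, but the point does not invalidate the study.

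**What to change.** Before any scan is read (C.1.a places reading after enrolment is complete), replace the blanket 0.05 rule for the four comparisons with 0% by a fixed sequence, each at two-sided 0.05. Start with PAV in the pooled set. Then list the other three in a stated order, with the reason for it, and test each only if the one before is significant. This holds the familywise error at 5% if the 0% reference is right. Holm across the four is an alternative if the sponsor does not want to commit to an order.

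Report the remaining models, including the lipid relationship that D.2 sets out to replicate, with nominal p-values labelled as not controlled for multiplicity.

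The cost is one paragraph and no new data. The fixed sequence has one downside: if an early step fails, the later ones go untested. The chance of that cannot be calculated for the stenosis steps, because the plan gives no stenosis effect size or SD. Those should be added, or the gap acknowledged. Holm avoids the ordering but raises the detectable pooled PAV difference at its first step from 0.51% to about 0.61%, with the loss of power after withdrawal depending on the unstated ICC.
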